3.0 Inclusion and Exclusion Criteria

3.1 Inclusion Criteria

- 1. Aged 21-70, verified by photo identification
- 2. Smoke ≥5 cigarettes per day for at least the past 12 months
- 3. Smoke regular, filtered cigarettes or machine-rolled cigarettes with a filter
- 4. Exhaled CO measurement ≥6 ppm at baseline visit
- 5. No serious quit attempt in past 7 days. This includes use of any FDA approved smoking cessation medication (varenicline, bupropion [used specifically as a quitting aid], patch, gum, lozenge, inhaler, and nasal spray) in the past 7 days as an indication of treatment seeking.
- 6. Willing to completely cease cigarette consumption and switch to an e-cig
- 7. Willing to attend regular visits over a 6week period (not planning to move, not planning extended vacation, no planned surgeries)
- 8. Able to read and write in English
- 9. Able to understand and consent to study procedures

3.2 Exclusion Criteria

- Unstable or significant medical condition in the past 12 months (recent heart attack or some other heart conditions, stroke, severe angina including high blood pressure if systolic >159 mmHg or diastolic >99 mmHg observed during screening)
- Severe immune system disorders (uncontrolled HIV/AIDS; unstable multiple sclerosis symptoms), respiratory diseases (exacerbations of asthma or COPD, require oxygen, require oral prednisone), kidney (dialysis) or liver diseases (cirrhosis), or any medical disorder/medication that may affect participant safety or biomarker data

- 3. Women who are pregnant (verified by urine pregnancy test at baseline visit), trying to become pregnant, or nursing
- 4. Use of any non-cigarette nicotine delivery product (pipe, cigar, cigarillo, dip, chew, snus, hookah, ecigs, strips, sticks) in the past 7 days
- 5. Use of an e-cig for 5 or more days in the past 28 days or any use in the past 7 days
- 6. Uncontrolled mental illness or substance abuse or inpatient treatment for these conditions in the past 6 months
- 7. History of a seizure disorder or had a seizure in the past 12 months
- 8. Currently or have ever taken medications prescribed to prevent seizures (such as Carbamazepine or Phenobarbital). Using seizure medications for off-label use (indications other than treatment for seizures) will not be included as an exclusion, these will be assessed on a case-by-case basis
- 9. Surgery (cardiac, thoracic, eye, ENT or abdominal) requiring general anesthesia in the past 6 weeks
- 10. Use of marijuana or any illicit drug/prescription drugs for non-medical use daily/almost daily or weekly in the past 3 months per NIDA Quick Screen
- 11. Use of hand-rolled, roll your own cigarettes
- 12. Known allergy to propylene glycol or vegetable glycerin
- 13. Other member of household currently participating in the study

3.3 Early Withdrawal of Subjects

3.3.1 Criteria for removal from study

The PI reserves the right to remove a participant from the study for any reason, based on their discretion.

3.3.1.1 Withdrawal prior to randomization

Participants who meet any criteria below at Visit 1 will be considered for withdrawal prior to randomization:

- Not smoking ≥35 cigarettes in past week
- Use of a non-cigarette nicotine delivery product in the past 7 days
- Reporting a quit attempt in the past 30 days
- Unable to provide a urine sample

3.3.1.2 General withdrawal criteria

Participants may be discontinued by the PI at any point during the study for any of the following reasons:

- **Missing their study visit window**: If a participant misses their study visit window, the participant will be considered for withdrawal from the study.
- **New pregnancy**: Participants who report a new pregnancy at any point during the study will be withdrawn.
- Suicide attempt: If at any time during the study it is discovered that a participant has made a suicide attempt, they will be withdrawn from the study.
- Cardiovascular disease (CVD) event requiring inpatient hospitalization: CVD typically includes MI (heart attack), PTCA (angioplasty/stenting), bypass surgery, stroke, peripheral vascular disease (arterial blockages in arms or legs leading to procedure or surgery). Less common CVD problems would be new cardiac arrhythmias (e.g., new atrial fibrillation) or new vavlular disease (e.g., mitral or aortic regurgitation).
- DVT/PE (deep vein thrombosis/pulmonary embolism, i.e., blood clots in the venous system) requiring inpatient hospitalization.

- Adverse events related to e-cig use: Adverse events will be monitored at every study visit.
- Worsening substance abuse in which the participant is behaving inappropriately at visits or demonstrates an inability to continue with the study.
- Any inpatient hospitalization or debilitation in which participation in the study could be detrimental to the recovery process. This will be self-reported by the participant and will be reviewed by the site PI and medical professional to determine whether continued participation in the study is appropriate (this could include recovery from a major surgery, worsening of psychiatric symptoms, etc.).
- Any situation where participant is not able to use their e-cig for a period of more than 2 weeks (e.g., incarceration or other similar situation) unless they report non-study product use by choice.
- **Participant choice**: Participants may choose to remove themselves from the study by informing the research team in writing at any point during the study. If they choose to remove themselves from the study, they will not receive any further contact from the study center.
- Inappropriate E-cig use: If a participant reports at any time that they have tampered with their research e-cig device or liquid or they have shared the device with others, the PI can withdraw the participant at their discretion. Also, if a participant reports at any time that they have used e-cig products not purchased from reputable sources, including products containing THC, they will be withdrawn.
- **Participant behavior**: If a participant is behaving in an inappropriate or threatening manner, admits to lying about eligibility criteria, is participating in other smoking research studies that could affect the primary outcome measures, appears/admits to giving away/selling study products, consistently loses study products etc., then the PI can withdraw him/her from the study at the PI's discretion.

3.3.2 Follow-up for withdrawn subjects

If participants are withdrawn from the study for any of the reasons noted above (in 3.3.1.1. or 3.3.1.2.) prior to randomization, they will be replaced until a total of 240 participants have been randomized to the study. Reasons for withdrawal will be ascertained from subjects who voluntarily withdraw from the study (End of Trial Form).

4.0 Recruitment Methods

4.1 Identification of subjects

All recruitment for this study will be routed through IRB STUDY00002213 which will also serve as the initial recruitment point of contact.

4.2 Recruitment process

Interested volunteers calling the study center number will first complete the eligibility script and questions for IRB STUDY00002213. If a participant's responses match this study's specified inclusion criteria they will be forwarded to research staff for further screening.

4.3 Recruitment materials

Recruitment materials used are the materials used in STUDY00002213:

4.4 Eligibility/screening of subjects

- Screening 1 (Phone): We will consider the screening process and eligibility questions in IRB STUDY00002213 as Screening 1. This process includes a brief phone screening to determine basic eligibility for any of our study center protocols. Then, participants will complete the screening for this study in two additional steps.
- 2. Screening 2 (Phone): Participants determined to be potentially eligible for the study will be contacted by researchers via phone, email, or text to complete additional screening. Those contacted via phone will complete the screening questions over the phone with the researcher, while those contacted by email or text will be provided a link to complete the screening questions online (https://redcap.ctsi.psu.edu/surveys/?s=TT37498THYA77JXK). A full script and screening questions, as well the email and text script, specific to this study are in the "Consent Forms and Recruitment Materials" section of the IRB application.
- 3. Screening 3 (In person, Visit 1): After a participant has met basic eligibility criteria over the phone, they will be scheduled to come into the study center where they will be re-screened (using Screener 2). If the participant's answers have changed from the phone screener (Screener 2) and they are no longer eligible, they will be informed that they cannot participate and they will be compensated for their travel via gift card (\$15). If they remain eligible, they will be consented to the study and further screened for eligibility. See section 7.2 for further details.

5.0 Consent Process and Documentation

5.1 Consent Process

5.1.1 Obtaining Informed Consent

5.1.1.1 Timing and Location of Consent

When participants attend their first in person assessment visit, they will have the study explained to them in detail, have the opportunity to ask questions, and then will be asked to sign the consent form. Participants will be given a signed copy of the form. This will take place in a private clinic room at the Penn State Clinical Research Center.

5.1.1.2 Coercion or Undue Influence during Consent

Once potential study volunteers are identified, they will be given information about the study and offered the opportunity to participate. The researchers obtaining consent will be instructed to clearly indicate that the participant's enrolling in the trial is purely voluntary and the researchers will not offer comments about whether they believe the participant should enroll in the study or not. Given the number of contacts and visits involved in the study protocol, the compensation provided to the participant is modest.

5.1.2 Waiver or alteration of the informed consent requirement

N/A

5.2 Consent Documentation

5.2.1 Written Documentation of Consent

An IRB-approved consent form will be used to document written consent. The participant will be given a copy of the signed consent. The participant's signed consent form will be uploaded into the participant's REDCap record.

5.2.2 Waiver of Documentation of Consent (Implied consent, Verbal consent, etc.)

Participants who are interested in the study will be asked to consent to allow the researcher to pre-screen them for the study over the phone by asking all screening questions of all participants (eligible or ineligible). Participants will be asked if this information can be retained so that the study team will know reasons that participants are not eligible for the study.

In addition, participants who are not eligible for the study, or those who begin the phone screener but are not interested in completing it after learning more about the study, will be asked if they would be interested in being contacted for future studies being conducted by our research team. They will be informed that by providing their name and phone number, they will be consenting to allow the study team to contact them in the future.

5.3 Consent – Other Considerations

- 5.3.1 Non-English Speaking Subjects N/A
- 5.3.2 Cognitively Impaired Adults N/A
 - 5.3.2.1 Capability of Providing Consent N/A
 - 5.3.2.2 Adults Unable To Consent N/A

5.3.2.3 Assent of Adults Unable to Consent N/A

- 5.3.3 Subjects who are not yet adults (infants, children, teenagers) N/A
 - 5.3.3.1 Parental Permission N/A
 - 5.3.3.2 Assent of subjects who are not yet adults N/A

6.0 HIPAA Research Authorization and/or Waiver or Alteration of Authorization

6.1 Authorization and/or Waiver or Alteration of Authorization for the Uses and Disclosures of PHI

Check all that apply:

Not applicable, no identifiable protected health information (PHI) is accessed, used or disclosed in this study. [Mark all parts of sections 6.2 and 6.3 as not applicable]

- Authorization will be obtained and documented as part of the consent process. [If this is the only box checked, mark sections 6.2 and 6.3 as not applicable]
- Partial waiver is requested for recruitment purposes only (Check this box if patients' medical records will be accessed to determine eligibility before consent/authorization has been obtained). [Complete all parts of sections 6.2 and 6.3]
- **Full waiver is requested for entire research study (e.g., medical record review studies).** [Complete all parts of sections 6.2 and 6.3]
- Alteration is requested to waive requirement for written documentation of authorization (verbal authorization will be obtained). [Complete all parts of sections 6.2 and 6.3]
- 6.2 Waiver or Alteration of Authorization for the Uses and Disclosures of PHI
 - 6.2.1 Access, use or disclosure of PHI representing no more than a minimal risk to the privacy of the individual
 - **6.2.1.1 Plan to protect PHI from improper use or disclosure** Information is included in the "Confidentiality, Privacy and Data Management" section of this protocol.
 - **6.2.1.2 Plan to destroy identifiers or a justification for retaining identifiers** All study data will be retained indefinitely.
 - 6.2.2 Explanation for why the research could not practicably be conducted without access to and use of PHI

The phone screener (Screener 2) will be used to check eligibility criteria (date of birth), and when participants are screened, their contact information will be used to follow-up about scheduling and for appointment reminders. This requires that we have complete contact (name, phone number) information.

6.2.3 Explanation for why the research could not practicably be conducted without the waiver or alteration of authorization

In order to screen the participants prior to inviting them into the study center, the investigators are conducting a phone screening to determine if the participants are likely to be eligible for the study.

6.3 Waiver or alteration of authorization statements of agreement

Protected health information obtained as part of this research will not be reused or disclosed to any other person or entity, except as required by law, for authorized oversight of the research study, or for other permitted uses and disclosures according to federal regulations.

The research team will collect only information essential to the study and in accord with the 'Minimum Necessary' standard (information reasonably necessary to accomplish the objectives of the research) per federal regulations.

Access to the information will be limited, to the greatest extent possible, within the research team. All disclosures or releases of identifiable information granted under this waiver will be accounted for and documented.

7.0 Study Design and Procedures

7.1 Study Design

This is a two-arm parallel-group, randomized, double-blind, placebo-controlled study.

7.2 Study Procedures

7.2.1 Screening (Phone)

All participants will be screened over the phone to ensure potential eligibility for the study. Those potentially eligible will be scheduled an in-person visit. Subjects will be instructed to smoke their usual brand of cigarettes normally for the next 7 days, avoid using any other tobacco products, and to tally the number of cigarettes smoked per day.

7.2.2 Baseline (Consent/Randomization) Visit – Visit 1 [Day 0]

The following procedures will be completed in a private clinic space in the Clinical Research Center. Participants and researchers will be wearing appropriate PPE at all times, except for noted measures where the participant will need to remove their mask (when COVID protocols apply).

(Part A): Consent and Confirm Eligibility

- **7.2.2.1** Prior to informed consent procedures, participants will complete the same screening questions that were completed over the phone previously (Screener 2 via phone) to confirm eligibility (at Visit 1). Participants will be asked to provide, for visual inspection, a photo identification to verify their age. Provided identification must be valid (ie. not expired), contain a photograph, a birthdate, and the name must match that of the participant. If participant meets eligibility criteria assessed via screening at Visit 1, they will continue with Visit 1 and be asked to provide informed consent. Otherwise, the participant will be compensated for their travel to the visit, and the End of Trial Form will be completed.
- **7.2.2.2** The participant will be provided with information about the study, will have the opportunity to ask questions, and will provide written consent to participate in the study. Participants will be provided with a copy of the consent form.
- **7.2.2.3** The following measures will be completed:
 - **7.2.2.3.1** Medical history will be documented. Those with any conditions listed as exclusion criteria will be excluded.
 - **7.2.2.3.2** Concomitant medication history will be recorded to ensure that the participant is not taking any medications that would exclude them from the study.
 - **7.2.2.3.3** The NIDA Quick Screen will be administered and participants indicating the use of prescription drugs for non-medical use/illicit drugs/marijuana daily/almost daily or weekly over the past 3 months will be excluded.
 - 7.2.2.3.4 Researchers will complete a 7 day timeline follow-back procedure to describe their cigarette use over the past 7 days. This is to confirm that the participant smoked at least ≥35 in the past week, and no quit attempts have been reported. If any of these criteria have not been fulfilled, the participant will be excluded.

- **7.2.2.3.5** Use of other tobacco products in the past 7 days will be assessed via Other Tobacco Use form. If the participant has used any other tobacco product in the past 7 days, they will be excluded.
- Participants will complete an exhaled carbon monoxide reading. Exhaled CO ≥6 ppm will be confirmed for inclusion in the study. Participants with a CO reading lower than 6 ppm will be excluded.
 - **7.2.2.3.6.1** When COVID protocols apply: Because this test requires that the participant remove their mask, the researcher will exit the room for this measure and will instruct the participant to complete the measurement via the two-way mirror and intercom system. Upon completing the measurement, the participant will be asked to put on their mask, and a timer for 15 minutes will be set as a guide for when the researcher may re-enter the room.
- **7.2.2.3.7** The participant will exit the clinic room to have their blood pressure measured. This is done in the small nursing station immediately outside of the clinic room. Participants with a blood pressure of systolic >159 mmHg or diastolic >99 mmHg will be excluded from the study.
- **7.2.2.3.8** Then the participant will have their height and weight measured.
- **7.2.2.3.9** Participants will then be taken to the CRC bathroom and will be asked to provide a urine sample. Participants unable to provide a urine sample will be excluded from randomization.
 - **7.2.3.9.1** Pregnancy exclusion will be confirmed through a urine test that will be self- administered by the participants when they come to this visit. Participants with confirmed pregnancy will be excluded.
- **7.2.2.4** The participant will then return to the clinic space. The researcher will remain outside the room to assess eligibility to continue with the study.
 - **7.2.2.4.1** If participants don't meet the eligibility criteria, they will be withdrawn from the study. They will be compensated for travel. The end of trial form will be completed. Eligible participants will continue with the study.

(Part B): Completion of Baseline Measures/Randomization

- **7.2.2.5** The 10 minute holter EKG procedure will be performed in the clinic space.
 - **7.2.2.5.1** When COVID protocols apply: This procedure will be completed once the clinic space is cleared for researcher entry (ie. 15 minutes after the CO measurement, measured using a timer).
- 7.2.2.6 Participants will then be randomized to a study group via REDCap.
- **7.2.2.7** Following randomization, participants will receive the assigned study product (SREC with 0 mg/ml nicotine liquid or SREC with 58 mg/ml nicotine liquid; researcher and subject are blind to the nicotine dose), which will be pre-prepared by the unblinded research staff.
 - **7.2.2.7.1** Participants will be provided 2 rechargeable e-cig batteries, 1 wall adapter, 1 USB charger cord, a user manual, and a supply of pods, based on the participant's cigarette smoking (up to 22 pods). In a case where the participant will run out of pods, the participant will be able to come to the study to pick up an additional supply.
 - **7.2.2.7.2** Research staff will then explain how to use the device.
 - **7.2.2.7.3** Participants will be advised to cease all tobacco use and to start using their assigned e-cig product beginning the next morning.
 - **7.2.2.7.4** Participants will be provided with smoking cessation resources that are available in the community, and they will be encouraged to use them. In

addition, participants will be given the document from the Centers for Disease Control and Prevention titled, "A Report of the Surgeon General: How Tobacco Smoke Causes Disease."

- 7.2.2.7.5
- 7.2.2.7.6 Participants will be instructed to complete daily diaries related to their study product and cigarette use (E-cigarette Daily Diary includes place to record cigarette use as well). They will also be asked to return all used or unused e-cig pods at their next study visit.
- 7.2.2.7.7 Pulmonary Function Testing (PFTs) PFTs will be conducted as described in the Time and Events Table at Visits 1, 2, and 3. Any significant worsening (10% worsening or greater) in pulmonary function will be documented as an adverse event. All adverse events will be documented and reviewed by the Medical Monitor within 5 business days. In cases where the medical monitor suspects that a participant may be having a respiratory adverse event related to the study, a pulmonologist ([name]) will be consulted. The pulmonologist will make any needed medical recommendations and a determination regarding whether the participant is able to continue with the study.
 - **7.2.2.7.7.1** When COVID protocols apply: The researcher will then leave the clinic space to complete the pulmonary function test, as the participant will need to remove their mask for this test. This will be facilitated by a two-way mirror and an intercom system. The researcher will remain outside of the clinic space for 15 minutes following the completion of this test and will use a timer to ensure that this time restriction is met.
- **7.2.2.8** Upon completion of the PFT test, participants will be given the opportunity to use the SREC device and ask the researcher any questions about its use prior to leaving the visit. The researcher will use the two-way mirror and intercom system to answer any questions.

(Part C): Visit Wrap-Up

- 7.2.2.9 Participants will then be provided with instructions to complete additional measures via a home computer/smart phone (see table of measures). A link to the surveys in REDCap will be sent to the participant's email address or phone. Participants will be instructed to complete all questionnaires within 24 hours. Participants unable to complete the questionnaires at home via a computer/smart phone will be called by the researchers to complete the questionnaires.
- **7.2.2.10** As the participant leaves the clinic space, participants will be provided with the Greenphire ClinCard.
 - **7.2.2.10.1** Once participants complete the additional questionnaires considered to be part of the visit (completed at home within 24 hours), they will be compensated for the visit. The funds will be automatically loaded onto the card.
 - **7.2.2.10.2** Those who do not complete the visit by completing the at-home questionnaires (which includes an option to opt-out of answering) will only be compensated for travel.

7.2.3 Switching Phase –Phone Contact #1 (Day 7 ± 7 days) and Phone Contact #2 (Day 14 ± 7 days) Note: While visit windows were extended to allow the participant flexibility, no visits (in person or phone), will occur on the same day.

During each phone contact, daily study product and cigarette use will be collected, adverse events or changes to concomitant medications will be documented, and participants will be asked to answer the measures indicated in the Time and Events Table. Participants will also be provided with advice/encouragement to remain abstinent from cigarettes. Participant's compensation for completing the phone call will be added to their gift card.

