7.2.4 Switching Phase – Visit 2 (Day 21 ± 7 days)

The following procedures will be completed in a private clinic space in the Clinical Research Center. Participants and researchers will be wearing appropriate PPE at all times, except for noted measures where the participant will need to remove their mask (when COVID protocols apply).

Prior to the visit:

7.2.4.1 Participants will then be provided with instructions to complete measures via a home computer/smart phone (see table of measures). A link to the surveys in REDCap will be sent to the participant's email address or phone the day of the clinic visit. Participants will be instructed to complete all questionnaires within 24 hours. Participants unable to complete the questionnaires at home via a computer/smart phone will be called by the researchers to complete the questionnaires.

(Part A): Participant Check-In

7.2.4.2 The following measures will be completed:

- **7.2.4.2.1** Adverse events will be documented, and any concomitant medication changes will be recorded.
- **7.2.4.2.2** The cigarette and study product use diary will be collected by the researcher and entered into Daily Cigarette and E-cig Use Diary Log in Redcap.
- **7.2.4.2.3** Use of other tobacco products in the past 7 days will be assessed via the Other Tobacco Use form.
- **7.2.4.2.4** Participants will be encouraged to remain abstinent from cigarettes.
- **7.2.4.2.5** Participants will be instructed to complete daily diaries related to their study product and cigarette use (E-cigarette Daily Diary). They will also be asked to return all used and unused e-cig pods at their next study visit.
- **7.2.4.2.6** Participants will be provided with a supply of pods based on their usage.

(Part B): Completion of Biomeasures

- **7.2.4.3** The participant will then leave the clinic space to have their blood pressure and weight measured.
- **7.2.4.4** Participants will then be taken to the CRC bathroom and will be asked to provide a urine sample.
 - 7.2.4.4.1 A pregnancy test will be completed for women of childbearing potential.
 - **7.2.4.4.2** Participants will complete an exhaled carbon monoxide reading.

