The first participants who meet the outlined criteria will be contacted by the researchers. We will continue to recruit participants for each category until all interviews for that category is completed. The interviews will be completed by blinded researchers but the management of the recruitment of participants for the interview will be managed by an unblinded study team member. This will ensure that recruitment for each category is correctly executed.

7.2.9 Follow-up Phase – Product Use Visit (Day 70 + 60 days) (Optional study visit)

At consent, participants will be given the option to be considered to participate in an additional study procedure. Participants who consent to the optional part of the study will be contacted by the researchers after completion of the study (after Visit Ph #5) to schedule the additional visit.

Participants who meet the following criteria will be contacted:

- Complete the study (ie. Complete Ph #5)
- Still using a nicotine containing product at Ph #5

The first participants who meet the outlined criteria will be contacted by the researchers. We will continue to recruit participants this optional visit until 10 participants have completed.

For the procedure, participants will be asked to use the SREC product in the lab while blood is collected. First, participants will be asked to abstain from any nicotine containing products for at least 14 hours before attending the visit. Once they arrive at the study center, a CO will be collected to verify abstinence (CO < 15 ppm to be eligible). Then, participants will complete

baseline questionnaires about withdrawal and craving. Then, participants will be given the SREC device with a 5% pod to use in the lab in a standard manner of 1 puff every 20 seconds for 14 puffs total (4 minutes, 20 seconds). Blood will be collected via an intravenous line at baseline and then 1, 2, 4, 6, 8, 10, 12 and 15 minutes after the first puff on the device. After the last sample is collected, the IV will be removed and participants will be asked to complete another CO measurement and to complete questionnaires about withdrawal and craving as well as questionnaires about their experience with the product.

	Time and Events Table									
	Baseline Phase	Switching Phase Follow-up Phase								
Study Week Number	0	1	2	3	4	5	6	10	10	10
Study Day	0	7	14	21	28	35	42	70	70	70
Study Visit Number	1	Ph #1	Ph #2	2	Ph #3	Ph #4	3	Ph #5	4 (ZOOM)	6
Measures/Questionnaires										

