COVID screening questions (day prior to visit)	x			Х			х			
Screening Questions	x									
Daily Cigarette and E-cig Use Diary	x	х	x	х	X	Х	х			
Past 7 day Cig and E-cig use								X	Х	
Other Tobacco Use	X	X	Х	Х	X	Х	X	X		
E-cig Patterns of Use and Log		X	Х	Х	X	Х	X	X		
Concomitant medications	X	X	Х	Х	X	Х	X	X		
Medical History	x	ĺ								
Cigarette Details	x									
Adverse events	X	X	Х	Х	X	Х	Х	X		
Demographics (Including Social Determinants of Health (SDOH))	x									
Tobacco use history	x									
Importance/Confidence to Quit	Х			Х		ľ	X	X		
NIDA drug screener (past 3 months)	x									
Environmental tobacco smoke	x			X			X			
Cigarette/E-cig perceived health risk	x			X						
E-cig Perceived Benefits and Harms	x									
Cigarette and E-cig Liking and Evaluation scales	x			X			x	x		х
Study Product Side Effects questionnaire		x	x	X	x	Х	x	x		х
Cigarette dependence (HONC, FTND, PSCDI)	x			X			x	x		
E-cig Dependence (Penn State E-cig DI)				X			x	x		
Questionnaire smoking urges	X	X	Х	Х	X	Х	X	X		х
Minnesota withdrawal scale	X	Х	X	Х	X	Х	Х	X		х
Audit-C	x						X			
CES-D	X			Х			Х			
Kessler K6	Х			Х			X			
Perceived stress scale	X			Х			X			

				0.	00100000	510
Clinical COPD questionnaire (CCQ)	X	X	X			
PROMIS Sleep Disturbance & Impact	x	X	X			
Interheart and WI Prepare	X		X			
Real World E-cig Use				Х		
Interview					Х	
Biomeasures/Procedures						
Weight	X	X	X			
Height	X					
Exhaled CO	X	X	X			x
Blood pressure/pulse	X	X	X			
Pulmonary function test (FEV1, FVC, PEF, FEF25, FEF75, FEF25-75, FET)	x	x	x			
Urine sample (NNAL, CYMA, MHBMA3, 3HPMA,8- isoprostanes, creatinine, cotinine)	x	x	x			
Holter EKG test (10 minutes)	X		X			
Pregnancy test	x	X	X			
Product use procedure			1			v

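### As Section 7.2.2 is written, the Visit 1 withdrawal and smoking-urge scores appear to be collected after randomization and offered SREC use, whereas Section 8.3 treats them as pre-randomization baselines.

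*Combined protocol and SAP*

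**What the plan says.** Section 7.2.2 sets out Visit 1 as an ordered list. Part A covers consent and eligibility measures. Part B, whose title refers to baseline measures and randomization, lists the Holter EKG and then step 7.2.2.6: "Participants will then be randomized to a study group via REDCap". The assigned product follows (7.2.2.7), and participants are told to stop tobacco and "start using their assigned e-cig product beginning the next morning". Pulmonary function testing comes next (7.2.2.7.7). In 7.2.2.8, "participants will be given the opportunity to use the SREC device and ask the researcher any questions about its use prior to leaving the visit".

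Part C, the wrap-up, then sends the home questionnaires: "Participants will then be provided with instructions to complete additional measures via a home computer/smart phone (see table of measures". Step 7.2.2.10.1 calls them "the additional questionnaires considered to be part of the visit (completed at home within 24 hours". Participants who cannot complete them online are telephoned.

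The Time and Events Table marks the "Minnesota withdrawal scale" and the smoking-urges questionnaire at Visit 1. In its text form it shows no clinic or home mark.

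Section 8.3 defines baseline as Visit 1 before randomization and says randomization falls at the end of that visit. Its first set of regressions controls for the baseline value of the outcome, and the same strategy is applied to MNWS and craving. Baseline MNWS and baseline QSU are also candidate covariates for the second set. Sections 1.1.2.2 and 1.3 describe the withdrawal and craving comparisons as controlled for baseline.

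**The concern.** Adjusting for a baseline score is safe because treatment cannot have affected it. That protection is lost if the score is taken after the participant has received, and perhaps used, a product that differs in nicotine between arms. The covariate may then carry part of the treatment effect, and adjustment removes that part from the later comparison. Randomization does not correct this.

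The route is plausible on the protocol's own evidence. Section 7.4.1 reports a peak nicotine level just over 21 ng/ml after 10 puffs in 5 minutes of the 58 mg/ml product. Withdrawal and craving are also the constructs that the product is hypothesized to change.

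At stake are the secondary withdrawal and craving comparisons, and any second-set model in which one of these two scores is retained.

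**Working it through.** **1. Order of steps.** The two sections compare as follows.

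| Item | Section 7.2.2 | Section 8.3 |
|---|---|---|
| Randomization | 7.2.2.6, in Part B | At the end of Visit 1 |
| Product hand-over, PFT, offered SREC use | 7.2.2.7 to 7.2.2.8 | Not mentioned |
| Home questionnaires | 7.2.2.9, in Part C, 24 hours allowed | Any Visit 1 score counts as pre-randomization |

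The two disagree for every measure collected under 7.2.2.9.

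**2. Are the two scales among those measures?** I counted the questionnaire rows marked at Visit 1 in the Time and Events Table.

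- Marked at Visit 1: 26.
- Tied to a step in 7.2.2: 6 (screening questions, diary, other tobacco use, concomitant medications, medical history, NIDA screener).
- Placed on the day before the visit: 1 (COVID screen).
- Not placed: 26 − 6 − 1 = 19, or 18 without adverse events.

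MNWS and smoking urges are among the 18. Step 7.2.2.9 is the only Visit 1 step that collects further questionnaires, and it points to the table. Elimination therefore puts both scales there. It does not prove it, because 7.2.2 is not a complete list: adverse events are marked at Visit 1 and have no step either.

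**3. Effect on the adjusted estimate.** Let D be the arm difference already present in the Visit 1 score and b the within-arm slope of the later score on it. Then

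E[adjusted difference] = true difference − b × D.

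The documents give neither b nor D. With b assumed at 0.4 to 0.6, each 1 point of D moves the estimate by 0.4 to 0.6 point, and D = 0 moves it by nothing. In SD units, with an assumed true difference of −0.50:

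| b | D | b × D | Adjusted difference |
|---|---|---|---|
| 0.4 | 0 | 0 | −0.50 |
| 0.4 | −0.10 | −0.04 | −0.50 + 0.04 = −0.46 |
| 0.4 | −0.25 | −0.10 | −0.50 + 0.10 = −0.40 |
| 0.6 | −0.10 | −0.06 | −0.50 + 0.06 = −0.44 |
| 0.6 | −0.25 | −0.15 | −0.50 + 0.15 = −0.35 |

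A simulation with 84 per arm and 20,000 runs agreed with the formula to within about 0.001, and the unadjusted estimate stayed at −0.50. The shift is toward no difference when the early and later effects share a sign, and away from it when they do not.

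**4. Precision lost by omitting the covariate.** The ratio of unadjusted to adjusted standard error is 1/√(1 − ρ²). At an assumed ρ = 0.4 it is 1/√0.84 = 1.091. At ρ = 0.6 it is 1/√0.64 = 1.250.

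**5. What is not affected.** The plan's only power figure concerns NNAL (Section 8.2). With 84 per arm, a difference of 35 and an SD of 69, z = 35/(69 × √(2/84)) = 3.287. Two-sided power at 5% is Φ(3.287 − 1.960) = 0.908, which meets the stated 90%. Urine, CO and blood pressure are taken in Part A and the Holter EKG before 7.2.2.6, so the first-set NNAL regression and the CO, blood pressure, EKG and cotinine baselines stand. The PFT follows randomization but precedes the SREC offer.

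**The case against.** The strongest reply is that nothing in the documents says these two scales are done at home. Section 8.3 states that baseline precedes randomization, and the step list is visibly incomplete, so the scales may already be given in Part A or Part B. This stands as a limit on certainty. It does not remove the conflict, because a reader who follows 7.2.2 literally finds no earlier place to administer them.

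Two supporting arguments are weak and the point does not rest on them. Visits 2 and 3 describe the home questionnaires under a pre-visit heading, but there too the link goes to the participant's "email address or phone the day of the clinic visit" with 24 hours to complete, so the contrast is largely one of headings. The optional product-use visit (7.2.9) does place "baseline questionnaires about withdrawal and craving. Then, participants will be given the SREC device", but it is a single laboratory session after enforced abstinence and says little about Visit 1.

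It is also fair that in-clinic use is only an opportunity, that the arms are blinded, and that regular use begins the next morning. Forms completed the same day without SREC use are probably little affected. They cannot be declared unaffected, because participants leave with the device.

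A reader might infer that these baselines are known to be contaminated, that the trial loses power, or that the primary result is biased. The documents support none of these. Collection time is inferred, D is unknown, no power is stated for these scales, and urine for NNAL precedes randomization.

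**Conclusion.** The concern holds as an unreconciled conflict between Sections 7.2.2 and 8.3. Followed as written, the visit appears to place the adjustment covariate for a baseline-controlled secondary comparison after randomization and after possible nicotine exposure.

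The order of steps and the Section 8.3 definition are explicit. The placement of MNWS and smoking urges is by elimination, so confidence is medium. The shift is b × D. Its size cannot be derived from the documents and may be zero; the figures of 0.4 to 0.6 point per point of D depend on assumed slopes. The change should be made, because the protocol does not at present show that these covariates are baselines.

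**What to change.** - Collect MNWS and smoking urges in clinic, after written consent and before 7.2.2.6. If this already happens, say so in 7.2.2.
- Mark clinic or home for each Visit 1 measure in the Time and Events Table, so that it, 7.2.2 and 8.3 agree.
- For participants already enrolled, report by arm how many Visit 1 scores were completed the same day and how many later. The REDCap audit trail (20.1.1) should allow this. Completion times will not show whether the SREC was used before answering.
- Add a sensitivity analysis in all participants that omits these scores as covariates. Do not exclude late responders, because completion time is itself a post-randomization variable.

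The cost is a little clinic time for two scales (the documents give no completion time), with no new measure. The sensitivity analysis is one extra model per outcome, with a standard error about 9% to 25% larger than that of a valid adjusted model at the assumed correlations of 0.4 to 0.6.
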